5.5 MBI Interpretation

MBI interpretation will be performed by study radiologists. The radiologists will subjectively assess BPU on a 5-category scale as 1 – photopenic, 2 – minimal, 3 – mild, 4 – moderate, or 5 – marked. Changes in BPU between pre-tamoxifen and post-tamoxifen MBI will be assessed, with blinding to the order of the studies.

The interpreting study radiologist will issue a report in the patient's medical record to state that the MBI was performed for research purposes under IRB #16-008736. The report will either state that no suspicious findings were noted, or will describe any incidental findings seen on MBI for which diagnostic workup is recommended. Any necessary diagnostic workup of MBI findings will be performed according to the established standard of care [17].

5.6 Low-dose tamoxifen intervention

Subjects will be enrolled to one of two arms of the study. The study arms will be identical, except for the dose of tamoxifen. For Arm 1, the dose of tamoxifen will be 5 mg per day for 30 days. For Arm 2, the dose of tamoxifen will be 10 mg per day for 30 days.

Participants will receive a prescription for tamoxifen. A physician co-principal investigator will order participant prescriptions, which will be filled through the Mayo Clinic Outpatient Research Pharmacy. For subjects in Arm 1, the research pharmacy will perform splitting of the standard tamoxifen tablets (available in either 10 mg or 20 mg doses) and over-encapsulation to arrive at 5 mg tablets.

Participant instructions for the tamoxifen medication will be as follows:

- Take one capsule per day for 30 days
- Take each dose at approximately the same time each day
- Capsules should be taken with water or a non-alcoholic beverage. Capsules can be taken with or without food.
- If you miss a dose, take the missed dose as soon as you remember it. However, if it is almost time for the next dose, skip the missed dose and continue your regular dosing schedule. Do not take a double dose to make up for a missed one.

Participants will also be given a "Drug Diary" log and asked to make notes of when each dose is taken and to record any symptoms experienced. Participants will be asked to return

Drug Diary logs and pill bottles at the Study Visit 2. Any remaining pills will be returned to the Outpatient Research Pharmacy for disposal.

Participants will be advised that they may elect to stop the tamoxifen medication at any time, should they experience unwanted side effects. Patients will be asked to contact study staff if they do choose to stop. Patients who start tamoxifen but choose to stop earlier than 30 days will be asked to return for their post-tamoxifen MBI test (Study Visit 2) at that time.

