1.3 Low-dose Tamoxifen

Tamoxifen is a selective estrogen receptor modulator (SERM) that blocks the effects of estrogen on breast tissue. Tamoxifen is FDA-approved as a chemopreventive option for both premenopausal and postmenopausal women. Studies have shown that preventive tamoxifen, when taken daily for five years, can reduce risk of developing breast cancer by at least one-third. Results from the National Surgical Adjuvant Breast and Bowel Project showed that in women considered at increased risk for breast cancer, preventive tamoxifen reduced breast cancer risk by approximately one-half [9]. However, at the standard clinical dose of 20 mg per day, tamoxifen can produce side effects such as menopausal symptoms, and also carries a small risk (<1% of participants) of serious adverse events, including uterine cancer and blood clots in legs or lungs. Concerns about the risk of these adverse events accounts for overall low utilization of tamoxifen for chemoprevention. In patients who do start tamoxifen, side effects of the drug can lead to non-compliance with long-term use.

Because of these concerns, multiple investigations have been done to determine efficacy of tamoxifen at lower doses. Tamoxifen taken at 5 mg per day has been proposed as an optimal dosage that is associated with decreasing biomarkers of breast disease (including mammographic density), and reduced breast cancer risk while potentially mitigating the adverse events and side effects seen at the 20 mg/day dose [10-12]. Other studies have evaluated efficacy of tamoxifen at 10 mg/day [13-15]. In one study conducted among women being treated for breast cancer, tamoxifen at 10 mg per day over a short period of 14 days resulted in clinically and statistically meaningful declines in molecular markers of estrogen receptor positivity, progesterone receptor positivity and Ki-67 (a marker of cellular proliferation) [15].

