5 STUDY PROCEDURES

5.1 Schedule of Evaluations

Potential participants will be screened for eligibility and undergo informed written consent with the study coordinator at the time of enrollment. At Study Visit 1, the participant will be asked to complete a study questionnaire and undergo MBI (after a negative pregnancy test as necessary). Participants will then undergo 30 days of low-dose tamoxifen medication followed by Study Visit 2, at which time a repeat MBI test will be performed.

	Enrollment	Study Visit 1	30 days between visits	Study Visit 2
Eligibility Checklist	X			
Informed Consent	X			
Questionnaire: Breast Health and History		Χ		
Blood pressure measurement		X		
Urine pregnancy test (if necessary)		Х		Х
MBI		Χ		X
Tamoxifen (5 mg/day for 30 days or 10 mg/day for 30 days)			X	
Check-in phone calls at day 5 and 20			Х	
Study close-out				X

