6.5 Risks of Tamoxifen

Tamoxifen has been used for over 40 years to treat hormone-receptor positive breast cancer. Side effects of tamoxifen taken at the standard 20 mg dose, ranging from mild to serious, have been reported. We expect side effects at the 5 mg or 10 mg dose to occur less frequently, if at all, especially over the short time frame of 30 days.

In patients taking standard 20 mg dose tamoxifen, vasomotor symptoms (hot flashes and night sweats) and vaginal discharge are the most likely side effects. However, in studies of women taking low-dose (5 mg or 10 mg) tamoxifen, hot flashes and vaginal discharge were not increased compared to women taking placebo.

Among women taking 20 mg tamoxifen for 5 years, there is a small increased risk of uterine cancer, abnormal blood clots, or vision changes. Other less serious side effects reported from 20 mg tamoxifen treatment include changes in menstrual cycle (among premenopausal women), weight gain, depression, insomnia, and urinary incontinence. These side effects are not expected to occur for short-term, low-dose tamoxifen used in this study.

Tamoxifen can cause birth defects. Participants who can become pregnant will undergo a pregnancy test prior to MBI, which must be negative. Participants will be instructed to avoid pregnancy during the study and for at least 2 months after study participation ends, by abstinence, barrier method, or nonhormonal contraception. If a participant should become pregnant, she will be instructed to stop using tamoxifen immediately.

7 ADVERSE EVENTS

Participants will be asked to report any adverse events or side effects, should they occur, by contacting study staff. At approximately days 5 and 20 of the tamoxifen intervention, the study coordinator will contact participants by phone to assess medication compliance and inquire about any adverse events. Adverse events will also be assessed at the study closeout during Study Visit 2. The duration and severity of adverse events will be recorded.

Although we do not expect serious side effects to occur with 5 mg tamoxifen over a 30-day period, patients will be advised to stop taking tamoxifen medication immediately if any of the following should occur:

- vision problems
- loss of appetite
- yellowing of skin or eyes
- unusual bruising or bleeding
- fever
- blisters

- rash
- swelling of eyes, face, lips, tongue, throat, hands, arms, feet, ankles, or lower legs
- thirst
- muscle weakness
- restlessness

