9 SAMPLE SIZE CONSIDERATIONS

There have yet to be any studies examining BPU response to tamoxifen. Thus, this study is a pilot design that will aim to enroll 30 patients who complete pre- and post-tamoxifen MBI. A sample size of 30 will have 80% power to detect a means change of 1 BPU quantitative unit (e.g. overall mean of 4.5 pre low-dose tamoxifen intervention, and post tamoxifen mean of 3.5), assuming a standard deviation of differences of 1.89 (effect size = 0.53), using a paired t-test with an α =0.05 two-sided significance level.

Allowing for potential study withdrawals, we will allow for a total of 50 patients to begin the low-dose tamoxifen intervention. In addition, women who are invited to participate may not have persistent BPU on their MBI performed at Study Visit 1. Prior pilot data showed that approximately half of women with prior high BPU had persistent high BPU on a current MBI. Therefore, up to 100 women will be screened with MBI to assess potential enrollment in the low-dose tamoxifen intervention. We will aim to balance enrollment of premenopausal and postmenopausal subjects.

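### No symptom record before the first capsule is described, so on-drug symptom reports cannot be separated from symptoms already present

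*Combined protocol and SAP*

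**What the plan says.** **Collection after dosing starts.** Section 5.6 gives each woman a Drug Diary along with her tamoxifen; she is "asked to make notes of when each dose is taken and to record any symptoms experienced". In Section 7, women are to contact staff about any adverse event, and "At approximately days 5 and 20 of the tamoxifen intervention, the study coordinator will contact participants by phone" to ask about compliance and events. Finally, "Adverse events will also be assessed at the study closeout during Study Visit 2". For each event, "The duration and severity of adverse events will be recorded". No rule is stated for onset, pre-existing symptoms, worsening or relatedness.

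**Before dosing.** The Section 5.1 table lists an eligibility checklist, consent, one form ("Questionnaire: Breast Health and History"), blood pressure, a pregnancy test if needed, and MBI. The form is completed at Study Visit 1, and its items are not given.

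**Expected effects and population.** Section 1.3 says that at the standard dose "tamoxifen can produce side effects such as menopausal symptoms". Section 6.5 says that at 20 mg "vasomotor symptoms (hot flashes and night sweats) and vaginal discharge are the most likely side effects", and expects fewer side effects at the study doses. Section 4.1 admits women from age 40. Section 9 adds: "We will aim to balance enrollment of premenopausal and postmenopausal subjects".

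**Stopping.** Section 7 lists symptoms for which women are advised to stop at once. They include thirst, restlessness, muscle weakness, rash, loss of appetite and vaginal bleeding or spotting. Hot flashes, night sweats and discharge are not listed. Under Section 5.6 a woman may also stop by her own choice because of side effects; she is then asked to come for the second MBI at that time.

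**The concern.** The main measurement has a within-woman baseline: BPU is imaged at Visit 1 and again at Visit 2. No matching baseline is described for symptoms. With no untreated group either, a hot flash noted on day 8 could be a drug effect or something the woman had every week before enrolment, and the described data do not tell these apart. The overlap is hard to avoid here. The population spans the menopause, Section 4.2 excludes systemic hormonal therapy in the preceding six months, and the side effects named in Sections 1.3 and 6.5 are ones that occur around menopause without the drug.

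Two things are at stake. One is the meaning of any adverse-event table that the study produces. The other is early stopping: several stop-list items are non-specific, and Section 7 does not say how an item already present before dosing is to be treated. A woman who stops for such a symptom has a shorter exposure before her second MBI. A pre-drug record cannot be reliably rebuilt once dosing has begun, so the gap has to be closed beforehand.

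**Working it through.** **1. The plan's own figure.** Section 9 gives n = 30, mean change 1, SD of differences 1.89, paired t-test, two-sided α = 0.05. Effect size = 1/1.89 = 0.529. Noncentrality = 0.529 × √30 = 2.90 on 29 degrees of freedom. Exact power from the noncentral t is 0.7998, which agrees with the stated 80%. No symptom quantity enters this calculation, so a symptom page changes nothing in it.

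**2. Timing of each described source.**

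| Source | Section | Relative to first capsule | Symptoms asked? |
|---|---|---|---|
| Eligibility checklist | 5.1 | before | items not shown; Section 4.2 covers conditions and drugs |
| Visit 1 questionnaire | 5.1 | before | items not shown |
| Drug Diary | 5.6 | after | yes, any symptom |
| Self-report to staff | 7 | after | yes |
| Calls, about days 5 and 20 | 7 | after | yes |
| Visit 2 close-out | 7 | after | yes |

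Every source described as asking about symptoms falls after dosing starts. The diary asks for any symptom, without limiting it to new or worse ones.

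**3. Comparator.** Arm 1 takes 5 mg and Arm 2 takes 10 mg (Section 5.6). There is no arm without tamoxifen.

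**4. Possible size.** The documents give no background rate, so the rate p is an assumption, taken from 10% to 50%. Expected reports with no drug effect = p × N.

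- N = 50 starters (Section 9): 0.10 × 50 = 5; 0.50 × 50 = 25.
- N = 30 completers (Section 9): 0.10 × 30 = 3; 0.50 × 30 = 15.
- Chance of at least one such report among 50 = 1 − (1 − p)^50. At p = 0.10 this is 0.995; even at p = 0.05 it is 0.923.

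These counts assume that every woman with the symptom reports it, so they are what could be reported rather than a forecast.

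**5. What a baseline would remove.** A symptom present at Visit 1 and no worse at Visit 2 drops out of a count defined as new or worse, so the 5 to 25 reports in step 4 would not enter it if those symptoms were stable. Symptoms that would have begun within the 30 days anyway stay in the count, because there is still no untreated group.

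**The case against.** The case against is substantial, and most of it limits how far the point goes.

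- *The questionnaire may already ask about symptoms.* This stands. One may say that no pre-drug record is described, not that none exists.
- *A reader might infer that existing symptoms will be counted as tamoxifen effects.* The documents do not support this. They contain no attribution rule and no adverse-event analysis, and Section 7 is worded in terms of events that occur, which is naturally read as onset on treatment. What can be said is that background and drug effect cannot be told apart.
- *A reader might infer that hot flashes will trigger the stop list.* They are not on it; they bear on stopping only through the woman's own choice. The 10% to 50% illustration therefore says nothing about how often treatment would end early.
- *A reader might infer that a stop loses the MBI pair or erodes power.* Section 5.6 asks women who choose to stop early to return for the second MBI then, and Section 9 allows 50 starters for 30 completers. Exposure is shortened, but the pair is not necessarily lost. No stopping rate is given, so no loss of power can be derived.
- *Section 4.2 partly screens for causes of stop-list items,* such as retinal disorders, anticoagulant use and endometrial disorders. True, but these are conditions and drugs, not symptoms, and thirst, restlessness or loss of appetite are not covered.
- *A reader might see a contradiction between Sections 4.2 and 7.* There is none: one sets eligibility, the other gives advice during treatment. The second simply leaves a case open.
- *Tolerability is not an objective, and a baseline page does not test the comparison with 20 mg.* Both are correct. They make this a modest point, but adverse events are collected, and they should be interpretable.

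**Conclusion.** The point holds in a limited form. As described, all symptom collection follows the first capsule and every participant takes tamoxifen, so on-drug reports of hot flashes, discharge, spotting or other listed symptoms cannot be separated from symptoms already present. At an assumed background rate of 10% to 50%, 5 to 25 of 50 starters could report such a symptom with no drug effect; that range rests entirely on the assumed rate and on complete reporting. A stop-list symptom already present could also lead to early stopping and a shorter interval on drug before the second MBI; the documents give no basis for putting a number on this.

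The BPU objective, the sample size and the stated 80% power are unaffected. If the Visit 1 questionnaire already records these symptoms, the data gap closes, and what remains is to say so and to define the reported event against that record. This is a cheap improvement worth making before dosing starts, not a fault in the main comparison.

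**What to change.** 1. State in Section 5.1 whether the Visit 1 questionnaire records current symptoms. If it does not, add one page, completed before the first capsule, listing the side effects in Section 6.5 and the symptoms in Section 7, each with severity.
2. Repeat the same page at Visit 2.
3. Add a sentence to Section 7 defining the reported adverse event as a symptom new or worse than at Visit 1, tabulated by arm and without causal claims.
4. Ask the investigators to clarify how the Section 7 list applies to a symptom already present at Visit 1. That decision is theirs, and no clinical rule is proposed here.

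Cost: one page at each of two existing visits, a few minutes per woman, and short additions to the text. No extra visit or arm is needed. The change does not replace a control group and does not allow a comparison with the 20 mg dose.

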5.7 Image Analysis

Quantitative assessments of BPU on all MBI studies will be performed by study staff using region of interest analysis. Counts within breast fibroglandular tissue and areas of fat in the breast will be obtained to calculate the ratio of counts per pixel in fibroglandular tissue vs. fat. Change in this ratio across MBI studies performed within patients will be determined.

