2 STUDY OBJECTIVE

To assess changes in background parenchymal uptake (BPU) on MBI before and after low-dose tamoxifen intervention (5 mg per day for 30 days or 10 mg per day for 30 days), among women with a history of high BPU. It is hypothesized that both subjective categorical and quantitative measures of BPU will decline with low-dose tamoxifen intervention.

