3 STUDY DESIGN

We propose a prospective clinical trial to be conducted within our cohort of women who have previously had an MBI test performed at Mayo Clinic. In this study, women with high

BPU on MBI will be invited to participate in a short-term intervention of low-dose tamoxifen (5 mg per day for 30 days or 10 mg per day for 30 days). MBI will be repeated at the end of the intervention. Change in BPU before and after the intervention will be assessed with both subjective and quantitative measures.

4 SELECTION AND ENROLLMENT OF PARTICIPANTS

The study population will include women who have no history of breast cancer and have previously had an MBI showing high BPU.

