If there is no evidence of infiltration on imaging of the injection site, the technologist will proceed with the breast images. If infiltration is confirmed by both low count rates and high uptake at the injection site, the technologist will ask for the patient's consent to proceed with a second injection of 8 mCi Tc-99m sestamibi. The patient will be given the option to refuse a second dose and continue with the study, although poor image quality may be obtained, or to discontinue MBI imaging and thus end study participation.

5.4.5 Image acquisition - MBI imaging will commence immediately after injection. Two views of each breast will be acquired in the CC and MLO projections. Acquisition duration will be 10 minutes per view. Images will be acquired in static mode using an energy acceptance window of 110-154 keV.

For each view, patients will be seated with the breast positioned between the two detectors. The persistence-scope should be used to validate correct breast positioning. If available, the recent mammogram can be viewed to replicate positioning on the MBI. Light compression is applied to stabilize the breast and to limit motion artifact. Placement of pillows behind the patient's back is recommended to reduce motion and increase comfort. Verification of the patient's comfort level and ability to complete 10 minutes of imaging in the position should be done before acquisition begins. Compression thickness for each MBI view will be recorded. At Study visit 2, the compression thickness for each view will be adjusted to match that recorded from the Study visit 1.

In participants with breasts larger than the detector field of view, the technologist may opt to acquire two 10-minute tiled MLO views of each breast, in place of a CC and MLO view, in order to ensure that the entire breast is included in the image set.

During the acquisition of each view, the technologist will briefly place the appropriate Co-57 laterality markers (R for right and L for left) in the field of view until well seen on the persistence screen.

The patient will be visually monitored by the nuclear medicine technologist from the time of injection of the radionuclide until image acquisition is completed.

5.4.6 Post-acquisition processing - Following completion of the acquisition, the technologist will format the acquired images in the standard format used for MBI display and interpretation.

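### Section 5.7 does not require the staff-measured fibroglandular-to-fat ratio to be read masked to visit, and the only blinding statement (Section 5.5) is not carried over to it

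*Combined protocol and SAP*

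**What the plan says.** The references are to the combined protocol and SAP.

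- **Section 2** predicts the direction of the result for both kinds of measure: "It is hypothesized that both subjective categorical and quantitative measures of BPU will decline with low-dose tamoxifen intervention".
- **Section 3** uses both kinds for the objective: "Change in BPU before and after the intervention will be assessed with both subjective and quantitative measures". Neither is named as primary.
- **Section 5.5 (MBI Interpretation)** describes the study radiologists' five-category reading and then says: "Changes in BPU between pre-tamoxifen and post-tamoxifen MBI will be assessed, with blinding to the order of the studies". This is the only mention of blinding in the supplied text.
- **Section 5.7 (Image Analysis)** gives the quantitative measure to other personnel: "Quantitative assessments of BPU on all MBI studies will be performed by study staff using region of interest analysis". Counts in fibroglandular tissue and in fat are turned into a ratio, and the change in that ratio within each patient is determined. Masking to visit, order or arm is not mentioned, and there is no reference back to Section 5.5.
- **Section 5.4.5** controls one visit difference when the images are acquired: "At Study visit 2, the compression thickness for each view will be adjusted to match that recorded from the Study visit 1".
- **Section 5.6** treats everyone: "The study arms will be identical, except for the dose of tamoxifen".
- **Section 9** names the only test, a two-sided paired t-test at 0.05, and powers it on a quantitative measure: "A sample size of 30 will have 80% power to detect a means change of 1 BPU quantitative unit".

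**The concern.** The ratio in Section 5.7 is not a machine reading. Someone decides which fibroglandular area and which fat area to sample, and the plan describes no automated or fixed-template placement that would remove that choice. An operator who knows which scan is post-treatment, and knows that a decline is expected, could place regions slightly differently at the two visits without intending to.

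In a trial with an untreated group, read by the same people without knowledge of group, a visit-related shift of this kind would affect both groups and largely cancel. Here there is no such group, and the analysis is a within-patient before-after difference. A shift in reading adds directly to the mean change and looks the same as a drug effect. A larger sample would not dilute it, because it is a systematic error and not a random one.

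The plan already treats knowledge of study order as a risk in Section 5.5, and it matches compression between visits in Section 5.4.5. It states no corresponding safeguard at the step where the quantitative value is produced. That value also appears to be the one the sample size rests on, since Section 5.7 describes the only quantitative measure of change in the plan.

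**Working it through.** **Inputs, all from Section 9:** 30 pairs, mean change 1 unit, SD of differences 1.89, paired t-test, two-sided alpha 0.05. The size of a reading shift is not given anywhere, so it is assumed below.

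**Step 1. Reproduce the plan's own figure.**
- Effect size = 1 / 1.89 = 0.529 (plan: 0.53).
- Noncentrality = √30 × 0.529 = 2.898, with 29 degrees of freedom.
- Power from the noncentral t distribution = 79.98% (plan: 80%). The figure reproduces.

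**Step 2. Threshold for significance with 30 pairs.**
- Standard error = 1.89 / √30 = 0.345.
- Critical t (29 df) = 2.045.
- Smallest significant observed mean change = 2.045 × 0.345 = 0.706 units.

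**Step 3. Effect of a reading shift when the drug does nothing.** Let the true change be 0 and let region placement move the mean difference by b units. The test statistic then has noncentrality b / 0.345, and the rejection probability is

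P(T > 2.045) + P(T < −2.045), with T noncentral t on 29 df.

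| Assumed shift b (units) | b / 1.89 (SDs) | b / 0.345 (noncentrality) | Two-sided rejection |
|---|---|---|---|
| 0 | 0 | 0 | 5.0% |
| 0.1 | 0.05 | 0.29 | 5.9% |
| 0.2 | 0.11 | 0.58 | 8.7% |
| 0.3 | 0.16 | 0.87 | 13.4% |

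**Step 4. What the table depends on.** It assumes that the quantitative unit of Section 9 is the ratio of Section 5.7, and that 1.89 is the SD of its change. The documents do not say so expressly. It also assumes the shift is systematic and in one direction. The table shows sensitivity and does not estimate bias.

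**Step 5. Does Section 5.5 already cover Section 5.7?** Two features favour a wide reading: the blinding sentence is passive and names no reader, and Section 3 says change is assessed by both measures. Three favour a narrow one: the sentence directly follows the radiologists' scale, it sits under the interpretation heading, and the ratio is described in a separate section, by different personnel, with no cross-reference. The narrow reading fits the layout better, but the text does not settle the matter.

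**The case against.** **The plan may already intend the blinding.** The Section 5.5 sentence speaks of changes in BPU generally. A sponsor could fairly say that it was meant for both measures. This stands as a possible reading, and it is why the point is put as a missing requirement. If it is what the sponsor means, one sentence in Section 5.7 settles it.

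**Silence is not evidence of unmasked measurement.** A reader might infer that staff will measure the scans knowing the visit. The documents do not say that. They only fail to require otherwise.

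**The size is invented.** No document gives a reading shift, the operator variability of the ratio, or its SD by name. The shifts of 0.2 and 0.3 units are 20% and 30% of the whole planned effect of 1 unit. At 0.1 units the rejection rate barely moves, to 5.9%. This objection stands in full. The case for masking rests on the design and on the low cost of the remedy, not on the table.

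**Masking does not rescue an uncontrolled before-after comparison.** This is correct. Women are selected for high BPU on an earlier MBI (Section 4.1), and Section 9 uses the Visit 1 MBI to assess entry to the intervention. Regression to the mean could therefore produce a decline however the images are read.

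**It is a pilot, with no decision rule attached to the test.** This is also true, and it limits the consequence. Section 1.4 nevertheless says the results will inform later study of BPU as a modifiable risk factor, so an avoidable ambiguity would be carried forward.

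**Conclusion.** The point holds as an omission that should be repaired. Section 5.7 assigns an operator-dependent main measure to study staff without requiring masking to visit, and the one blinding statement in the plan is not clearly extended to it. With all participants treated and a paired before-after test, any visit-related shift in region placement would enter the mean change and could not be separated from a drug effect.

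The size is unknown. If the SD of 1.89 applies to the ratio and the true change is zero, assumed shifts of 0.1, 0.2 and 0.3 units with 30 pairs give rejection rates of 5.9%, 8.7% and 13.4% in place of 5%.

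Two stronger conclusions should not be drawn. The first is that the quantitative result will be biased, or that the trial's false-positive rate is 13.4%; this would need evidence of a shift, and the documents contain none. The second is that the Section 5.5 reading is itself inadequately blinded. Order blinding is stated there, and nothing in the text shows that the clinical report feeds into the assessment of change.

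**What to change.** Add to Section 5.7 that region-of-interest measurement for the change analysis is done on images stripped of date and visit identifiers, in random order, by existing study staff who do not know which study is pre- or post-tamoxifen. This extends the Section 5.5 order blinding to the quantitative measure.

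Section 5.7 covers all MBI studies, and Section 9 allows up to 100 women to be scanned but only 50 to start tamoxifen. The added text should therefore also say how studies from women with only a Visit 1 MBI are handled. They can be mixed into the same masked batch or measured separately, since they do not enter the paired change.

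The cost is some image preparation, and measurement for the change analysis waits until both studies of a participant exist. No new scans are needed, and the sample size and power calculation are unchanged. The documents do not say who measures the regions or whether they also run visits, so the sponsor should confirm that suitable staff are available.

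This removes only the reader's part of any visit effect. Regression to the mean and other before-after effects remain and need to be acknowledged when the change is interpreted.
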